#### 5.3.3.1 Preparation of Test Areas on Treatment Day

A Test Site Diagram for the inguinal test area is shown in Appendix 14.7.

The test area within the inguinal region is defined as the uppermost inner aspect of the thigh (the groin), centering the long axis of the template along the inguinal crease immediately below the

3M Confidential

Document Name: CLIN-PROT-ICH-US-05-658998

Clinical and Non-Clinical: CLIN-INDEX-3M-SPON-US-05-014624

**[name]**

groin. If, due to a subject's anatomy, the test area cannot be centered along the inguinal crease, the area should be positioned on the upper, inner thigh as close to the crease as possible. In no instance should sampling be performed on areas not having skin-to-skin contact. Using a 1.5" x 5" sterile template, the corners of each inguinal test area will be marked directly on the skin using a non-toxic skin marker. Four sampling sites will be numbered within each inguinal test area. The positioning and numbering of the inguinal sampling sites are standard for all subjects. Sampling sites on the contralateral side of the groin will be numbered in a mirror-image orientation. The 4 sampling sites within each inguinal test area represent one baseline (pre-prep) site, 2 post-prep sample sites (10-min, 6-hr), and an unused site. Sampling sites 2, 3 and 4 will be randomized as baseline and the 2 post-prep sample sites. Sampling site 1 is designated as the unused sample site.

After inguinal test areas are marked and sample sites are numbered, baseline samples will be collected from the right and left test areas per the randomization schedule using the cup scrub technique described in Section 5.3.4.1.

### **5.3.3.2 Study Product Application**

Following baseline sample collection, the contralateral inguinal test areas will each be prepped with 1 of the 3 study products according to the randomization codes provided. Treatments will be randomized between left and right test areas and post-prep sampling times will be randomized amongst the sampling sites within a test area.

The study products will be applied per the randomization schedule and the Investigational Product Application Instructions (Appendix 14.2). The duration of each prep procedure will be recorded on the appropriate form.

### **5.3.3.3 Evaluation of Skin Irritation**

Prior to collection of the baseline, 10-minute, and 6-hour post-prep samples, the skin in each test area will be evaluated for indications of skin irritation, based on the Skin Irritation Rating Scale (Appendix 14.8). Skin irritation ratings for each area will be recorded on the Skin Irritation Rating form. A rating of 3 in any category during the evaluations for the 10-minute, and 6-hour post-prep samples represents significant irritation and qualifies as an Adverse Event. Any area with a rating of 3 should not be sampled.

### **5.3.3.4 Timing of Post-Prep Sample Collection**

Microbial samples will be collected at 10 minutes ( $\pm$  30 sec.) and 6 hours ( $\pm$  30 min.) post-prep from the groin. Post-prep timing begins upon completion of study product application, including the 3-minute drying time. Microbial samples will be collected using the cup scrub technique described in Section 5.3.4.1.

After the 10-minute post-prep samples have been collected, a sterile non-occlusive dressing will be secured over the remaining sample sites to allow subjects restricted mobility and to protect the

3M Confidential

Document Name: CLIN-PROT-ICH-US-05-658998

Clinical and Non-Clinical: CLIN-INDEX-3M-SPON-US-05-014624

[name]

sites from contamination between sampling times. The subjects will be allowed to leave the clinical test facility as long as they return within 6 hours for collection of the 6-hour samples. Subjects should be reminded that they are to avoid showering, tub-bathing, swimming, vigorous physical activity that may cause sweating, and any other activities that may compromise the integrity of the test sites until their final sample collection has been completed. In the event that the dressing on the 6-hour test site has been compromised, the site will be sampled and the loss of dressing integrity will be recorded on the appropriate DCS.

Following the final sample collection, residual study products will be removed from the subject's skin with alcohol wipes.

### **5.3.4 Microbiological Methods**

#### **5.3.4.1 Sample Collection and Processing**

Quantitative cultures will be obtained from test sites using a modification of the cup scrub method of Williamson and Kligman. Modified sampling solution (MSS) will be used to collect all microbial samples.

##### Modified Sampling Solution (MSS):

A sterile scrub cup will be placed and held firmly on each site. **Scrub 1:** 1.0 mL of Triacetin and 2.0 mL of SSS will be aseptically pipetted into the scrub cup. The skin will be scrubbed in a circular motion with moderate pressure for 1 minute using a sterile policeman. Using a sterile transfer pipette, the scrub solution will be transferred to a sterile collection tube. **Scrub 2:** An additional 3.0 mL of fresh SSS will be pipetted into the scrub cup and the scrub procedure will be repeated. This solution will be pooled with the solution from Scrub 1 for a total sample volume of approximately 6 mL per site.

Following collection, each sample tube will be capped tightly and pulsed 3 times on a vortex mixer followed by a 2-minute sonication and 30-second vortex. A 1.0 mL aliquot of each sample will be diluted into sterile tubes containing 9.0 mL PBW. Serial 10-fold dilutions will be performed in PBW. One-milliliter (1.0-mL) aliquots of selected dilutions will be pour-plated in triplicate using TSA+N. **Samples must be plated within 30 minutes of collection. Plated samples must be well swirled.** Each plate should be labeled with the subject treatment number, anatomical region sampled (groin), test site sampled (right or left and time point), and dilution plated. After 72 ( $\pm$  4) hours of aerobic incubation at  $30 \pm 2^\circ\text{C}$ , colonies will be counted and viable cells in the original sample will be calculated using standard methods. Following incubation, plates may be refrigerated for up to 48 hours prior to counting.

#### **5.3.4.2 Collection of Raw Data**

Raw colony counts from each of the dilutions will be recorded on the appropriate DCS for each subject.

**[name]**

Based on the scrub and dilution process, in order to have a baseline  $\geq 5.0 \log_{10}$  requires that the average of the 3 plates from the  $10^{-3}$  dilution be  $\geq 63$ . Averaging of the Screening Day counts will be automatically performed on the eCRF upon entry of raw data and Clindex will determine the subject's eligibility for treatment.

#### **5.3.4.3 Neutralization of Investigational Materials**

The effectiveness of the neutralizers contained in the microbial sampling solution will be tested based on ASTM E1054-08 (Reapproved 2013), Standard Test Methods for Evaluation of Inactivators of Antimicrobial Agents, prior to Treatment Day. The Protocol for Validation of Neutralizer Effectiveness is provided in Appendix 14.9.

#### **5.4 Subject Discontinuation**

The Investigator or designee may discontinue individual subjects from the study at any time. Subjects may voluntarily withdraw from the study at any time. The Investigator or designee will provide a written report on the appropriate form including the date and reason for discontinuation. Subjects who have been previously screened may not be re-entered into the study.

#### **5.5 Subject Revocation of Authorization to Use and Disclose Protected Health Information**

In order to implement a valid revocation of authorization, the subject or their representative must make the request in writing to Microbac Laboratories, Inc., [name]. The revocation cannot stop the use or disclosure of information that has been collected and disseminated prior to the revocation, is needed to ensure complete and accurate study results, and is required by law or government regulation (eg, reporting adverse events). Revocation of an authorization may not be used to withhold normal medical care from the subject but may make the subject ineligible to receive the study treatment or care.

### **6. ASSESSMENT OF EFFICACY**

#### **6.1 Efficacy Parameters**

Non-inferiority of the investigational product to the FDA-approved active control for  $\log_{10}/\text{cm}^2$  recovery of skin flora relative to Treatment Day baseline  $\log_{10}/\text{cm}^2$  on the inguinal region at 10 minutes following application. Non-inferiority is based on a non-inferiority margin of 0.5  $\log_{10}/\text{cm}^2$ .

Superiority of the active products to the negative control for  $\log_{10}/\text{cm}^2$  recovery of skin flora relative to Treatment Day baseline  $\log_{10}/\text{cm}^2$  on the inguinal region at 10 minutes following application. A superiority margin of 1.2  $\log_{10}/\text{cm}^2$  is used.

**[name]**

Number of observations for which the  $\log_{10}/\text{cm}^2$  recovery of skin flora on the inguinal region at 6 hours following application of the study products is higher than treatment day  $\log_{10}/\text{cm}^2$  baseline skin flora.

## **6.2 Assessment Methods**

Efficacy will be assessed by sampling the skin using the cup scrub method described in Section 5.3.4.1.

# **7. ASSESSMENT OF SAFETY**

## **7.1 Safety Parameters**

The principal measure of safety will be the incidence of adverse events reported during the study and a summary of the skin irritation rating scores. A skin irritation rating of 3 post-treatment in any category represents significant irritation and qualifies as an Adverse Event.

## **7.2 Assessment Methods**

The Investigator or designee will assess the subject's skin condition prior to collection of the baseline, 10-minute, and 6-hour post-prep samples using the Skin Irritation Rating Scale (Appendix 14.8).

## **7.3 Adverse Events**

The Investigator is responsible for identifying adverse events that occur to each subject on Treatment Day. An adverse event can be identified by the Investigator or reported by the subject.

Note: The Federal Privacy Rule (HIPAA) specifically permits the use and disclosure of protected health information "without written authorization of the individual" when used for public health activities such as reporting adverse events, tracking FDA-related products, enabling recalls, repairs, replacements, lookbacks, or conducting post-market surveillance. This use and disclosure is subject to the *minimum necessary* standard, ie, "the minimum necessary to accomplish the intended use, disclosure, or request."

## **Definitions**

- Adverse event (AE) means any undesirable clinical occurrence in a subject whether or not it is considered to be drug related.
- Drug-related adverse event (ie, adverse drug experience) is an adverse event that is considered by the Investigator to have a reasonable likelihood of being associated with the investigational drug.
- Life-threatening adverse drug experience is any adverse drug experience that places the subject, in the view of the Investigator, at immediate risk of death from the reaction as it

**[name]**

occurred (does not include a reaction that, had it occurred in a more severe form, might have caused death).

- Serious adverse drug experience is an adverse drug experience that is fatal or life-threatening, is permanently or significantly disabling/incapacitating, requires inpatient hospitalization or prolongation of existing hospitalization, or results in a congenital anomaly/birth defect.
- Unexpected adverse drug experience is one not previously identified in nature, severity or frequency of incidence in the current Investigator brochure, in the clinical plan, or elsewhere in the current IND application and amendments.

### Recording and Reporting

The Investigator records each AE occurring in the study, including those not thought to be associated with the drug, on the Adverse Event Record. Documentation includes the AE description, severity at onset, seriousness, date of onset and resolution, relationship to the investigational drug, action taken, and outcome.

The Investigator must promptly report all adverse drug experiences to the 3M study monitor. If the adverse drug experience is also considered by the Investigator to be serious and/or unexpected the Investigator must report it to the IRB as soon as possible.

3M reports (by telephone or fax) a death or life-threatening adverse drug experience to the FDA within 7 days of notification and submits a follow-up report within 15 days.

A serious and unexpected adverse drug experience involving a non-3M commercialized product is reported to the 3M study monitor and IRB.

If a subject does not experience an AE during the study, the absence of such must be recorded on the form.

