9.1 Adverse Events

All adverse events (AEs) occurring after initiation of study treatment (treatment emergent AEs) will be summarized by severity, relatedness, overall and by treatment group. AEs occurring during the screening period will be summarized separately. All AEs will be classified using the MedDRA dictionary.

All verbatim descriptions will be listed for all AEs, along with information regarding onset, duration, severity, relationship to treatment, and action taken.

Serious adverse events will be summarized and presented according to nature, time to onset, duration, relationship to treatment and outcome.

A Fisher's Exact test will be carried out to compare each safety parameter between the treatment groups.

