### **1.4 Good Clinical Practices and Regulatory Requirements**

3M™ SoluPrep™ Preoperative Skin Preparation is an investigational new drug. This study will be conducted in compliance with the protocol, Good Clinical Practice (GCP), and applicable state and federal regulations including 21 CFR 312 (Investigational New Drug Application), 50 (Protection of Human Subjects), 56 (Institutional Review Boards), 54 (Financial Disclosure by Clinical Investigators), and 45 CFR 160 and 164 (Authorization for Use/Disclosure of Protected Health Information).

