## **3. STUDY DESIGN**

### **3.1 Study Type and Methodology**

This is a randomized, controlled, third-party blind, single-center study in healthy volunteers where each subject receives 2 of the 3 possible study products on the groin. The study staff performing the bacterial enumeration and the statistician performing the analysis will be blinded to the study products.

Table 3.1A provides a summary of the study procedures. A schematic diagram of the study is included in Appendix 14.1.

[name]

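### Protocol 7.3 frames AE causality only against the investigational drug and names no test side, although every subject carries two products and SAP 9.1 needs relatedness by treatment group

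*Combined protocol and SAP*

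**What the plan says.** Design: under protocol 3.1, "each subject receives 2 of the 3 possible study products on the groin". The combinations are SoluPrep + SoluPrep FF, SoluPrep + saline, and SoluPrep FF + saline, allocated 6:1:1 (SAP 3.2).

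Causality: the Definitions in protocol 7.3 make an AE drug-related when it is "considered by the Investigator to have a reasonable likelihood of being associated with the investigational drug". Recording and Reporting in the same section lists what AE documentation includes, and the list ends with "relationship to the investigational drug, action taken, and outcome". On which product is meant, protocol 1.4 says "3M™ SoluPrep™ Preoperative Skin Preparation is an investigational new drug". SoluPrep FF is described as an approved product (protocol 1.1 and 2) and is supplied in its marketed packaging (protocol 3.4.3).

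Analysis: SAP 9.1 says that treatment-emergent AEs "will be summarized by severity, relatedness, overall and by treatment group". It also plans a listing that shows relationship to treatment, and a Fisher's exact test of each safety parameter between treatment groups. Protocol 8.2.2 asks for AE summaries by product.

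Reporting: beyond the rules for adverse drug experiences in general, protocol 7.3 adds one sentence for control products: "A serious and unexpected adverse drug experience involving a non-3M commercialized product is reported to the 3M study monitor and IRB".

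**The concern.** The causality question in protocol 7.3 would suit a trial in which each subject receives one product. Here each subject carries two, and some carry two without the investigational one. An investigator who follows the text could judge a reaction under SoluPrep FF or saline to be clearly caused by that product and still have to record it as unrelated to the investigational drug. The SAP then needs a relatedness count for each treatment group from an item that was not asked about two of the three products.

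AE incidence is part of the principal measure of safety (protocol 7.1), and a reader will want to set SoluPrep beside its active control on related events. If side and per-product causality are not recorded when the event occurs, they are hard to reconstruct after data lock.

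**Working it through.** No sample size, power or alpha in the plan depends on this point, so there is no stated figure to reproduce. The check compares the relevant sections and then counts the subjects affected.

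**Sections side by side**

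- *What is asked.* Protocol 7.3 names one causality item, against the investigational drug. It names no test area and no second causality item.
- *What is needed.* SAP 9.1 needs relatedness by treatment group, and protocol 8.2.2 needs AEs by product.
- *How the two are linked.* Neither document says how an AE is assigned to one of a subject's two products. SAP 5.1 analyses safety by randomised group. In the protocol's example randomisation table, treatment group is the combination (1 to 3), not a product. Whether the AE table has combinations or products as its columns is therefore open.
- *What can be recovered.* Protocol 5.3.3.3 has irritation rated and recorded for each test area, and protocol 3.3 has the product on each side recorded. A rating of 3, which counts as an AE, can therefore be tied to a side and its product.
- *What cannot be recovered from the named fields.* The irritation scale (Appendix 14.8) covers erythema, edema, rash and dryness. Protocol 1.3 also anticipates itching, cracking and peeling, which have no category of their own on the scale. Those events, other local AEs and all systemic AEs rely on the AE record.
- *Reporting.* An adverse drug experience is by definition tied to the investigational drug, and the extra sentence covers only other manufacturers' marketed products. The sponsor's own marketed SoluPrep FF, read literally, falls under neither.

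**Subjects affected**

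Inputs: allocation 6:1:1 (SAP 3.2); 135 subjects expected to be treated and 115 needed (protocol 1.5); 10 blocks of 12-2-2, which is 10 × 16 = 160 (protocol 3.3).

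- Share with no SoluPrep = 1/8 = 12.5%. Of 135: 135 × 1/8 = 16.9, about 17. Of 115: 14.4, about 14. Of 160: 20.
- SoluPrep FF subjects of 135 = 135 × (6 + 1)/8 = 118.1. Those who also have SoluPrep = 135 × 6/8 = 101.25. Ratio = 101.25/118.1 = 6/7 = 85.7%.
- Saline subjects of 135 = 135 × (1 + 1)/8 = 33.75. All carry an active product as well, half of them SoluPrep and half SoluPrep FF.

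The shares do not depend on the total enrolled. For the 12.5% with no SoluPrep, the causality item has no literal meaning. For a systemic AE in the 6/7 of SoluPrep FF subjects who also carry SoluPrep, no tabulation by product can separate the two.

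**The case against.** The strongest reply is that protocol 7.3 gives an open list and the AE record itself is not among the documents. The form may hold a side field, the free-text description may name the side, and SAP 9.1 lists every verbatim description. This stands in part: one cannot say that side is never captured, only that the protocol does not provide for it. A field that the analysis needs should not rest on free text or on an unseen form.

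Second, the protocol uses the word investigational loosely. The SoluPrep FF steps in Appendix 14.2 call it the investigational product, the disposition form in Appendix 14.4 uses similar wording for every study product, and SAP 9.1 speaks of relationship to treatment. The intended scope may therefore be wider than SoluPrep. That is fair, but the definition and protocol 1.4 point the other way, so the ambiguity itself needs settling.

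Third, treatment group may mean combination, in which case SAP 9.1 already tabulates non-local AEs in a workable way. That is possible, but protocol 8.2.2 says by product.

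Fourth, all AEs are recorded whether or not they are thought to be related, so the overall AE count does not depend on causality coding. This stands. Safety is also a secondary objective with no success criterion.

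A reader might infer something stronger: that SoluPrep FF and saline must show zero related events, so that the relatedness comparison is biased against SoluPrep and cannot be valid. The documents do not support that. It needs the narrowest reading of the causality item together with correct assignment of each event to a side, and the second condition conflicts with the complaint that side is not named. If events were counted by subject instead, a SoluPrep-related AE in a SoluPrep + SoluPrep FF subject would also appear under SoluPrep FF. Nor does the SAP name relatedness as something to be tested.

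**Conclusion.** The point holds as a mismatch between what protocol 7.3 provides for and what SAP 9.1 and protocol 8.2.2 require. Relatedness is not assured for SoluPrep FF or saline, is undefined for 12.5% of subjects (about 17 of 135), and cannot be split by product for non-local AEs in the 6/7 of SoluPrep FF subjects who also receive SoluPrep. Rating-3 irritation events can be located by side, so what remains is their causality coding, other local AEs and systemic AEs. As worded, the reporting paragraph also leaves SoluPrep FF without an explicit route.

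This rests on two assumptions: that investigational drug means SoluPrep, as protocol 1.4 indicates, and that the AE record follows the list in protocol 7.3. The direction and size of any error in the related-AE counts cannot be derived from the documents. The change should be made before data collection, but the efficacy conclusions do not depend on it.

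**What to change.** - **Protocol 7.3, recording:** add AE location (left test area, right test area, systemic/other), and relationship to the product on the left and to the product on the right. Define drug-related against any study product.
- **SAP 9.1:** tabulate local AEs by the product on the affected side and non-local AEs by treatment combination (1 to 3). State which of these treatment group means in each table, and use the same causality term as the protocol.
- **Protocol 7.3, reporting:** reconcile the definitions with the reporting paragraph so that events related to SoluPrep FF fall under a stated route.

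The cost is a few fields on the AE form and a few sentences in each document, with no extra visits or procedures. The investigator is not blinded to the products (protocol 3.3) and can complete the fields when the event occurs.

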## 8. STATISTICS

### 8.1 Sample Size Justification

The Final Monograph (21 CFR Part 310 Safety and Effectiveness of Health Care Antiseptics; Topical Antimicrobial Drug Products for Over-the-Counter Human Use) calls for a minimum of 100 observations per treatment. A standard deviation of  $1.0 \log_{10}/\text{cm}^2$  was observed in study EM-05-012760. One-hundred subjects per treatment arm provides 94% power using a non-inferiority margin of  $0.5 \log_{10}/\text{cm}^2$  with a 1-sided alpha of 0.025.

In the same study, a superiority to the negative control was observed to be approximately  $2.5 \log_{10}/\text{cm}^2$ , with a lower 95% confidence bound of  $2.26 \log_{10}/\text{cm}^2$ . A sample size of 30 for the negative control will ensure that the mean for  $\log_{10}/\text{cm}^2$  reduction of skin flora relative to

[name]

Treatment Day baseline will be normally distributed. Power was assessed through simulation using an assumed superiority of  $2.26 \log_{10}/\text{cm}^2$  (the lower 95% confidence bound observed in study EM-05-012760), sample sizes of 30 for the negative control and 100 for the active treatments, and the standard deviation of  $1.0 \log_{10}/\text{cm}^2$  mentioned above. All 1000 simulations had a lower bound for superiority greater than  $1.2 \log_{10}/\text{cm}^2$ .

